10.2.4 End-of-treatment Visit

Visit following the completion of dressing securement at the insertion site after removal of DVC. A patient who has multiple catheters withdrawn during the trial should be documented sequentially, but the trial is not to be considered complete at least until the CVC is removed. If replacement of the same type of DVC is performed, only the first removal is recorded and the subsequent replacement is not included in the test or observation.

The following procedures will be completed during the end-of-treatment visit:

1. Assessment of dressing securement performance;
2. Assessment of skin conditions around the catheter site, with reference to the standards for evaluating local skin irritation as listed in the appendix;
3. Photographic documentation of any anomalies;
4. Following departmental routine practice, the tip is cut with sterile scissors after removal, while skin sampling around the insertion site is performed. The samples taken are, under aseptic conditions, sent for pathogenic bacteria testing and species analysis.
5. In case of suspected CLABSI/CRBSI occurrence, sampling and quantitative culture for both catheter and peripheral blood will be performed simultaneously, as well as analysis of pathogenic bacteria species, according to diagnostic evaluation criteria.

The following data will be collected during the end-of-treatment visit:

1. Vital signs: Pulse, blood pressure, respiratory rate, body temperature;
2. Relevant laboratory tests, including blood routine examination: Red blood cell (RBC) count, white blood cell (WBC) count, neutrophil ratio, hemoglobin, platelets, C-reactive protein, etc.;
3. Documentation of dressing securement performance;
4. Documentation of skin conditions around the catheter site, including erythema, edema, rash, etc., and scoring with reference to the standards for evaluating local skin irritation as listed in the appendix.

5. Total duration of DVC placement and duration of application of the test/control dressing;
6. Catheter-tip culture and classification of colonies;
7. Culture and classification of colonies from the skin samples around the insertion site;
8. Any changes in medication use relevant to the trial, including mainly fat emulsions, heparin, blood transfusions and antimicrobial drugs;
9. Confirmation of CLABSI/CRBSI diagnosis;
10. Adverse events, device defects, complaints.

Any Adverse Events, which are not safety related, and which are ongoing at the end of the study, should be marked as ‘persistent’ per study-specific CRF.

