2.1 Description of Study Device

3M™ Tegaderm™ CHG I.V. Securement Dressing consists of a transparent dressing and a gel pad. The gel pad contains 2% (w/w) chlorhexidine gluconate (CHG). CHG is a classical germicide with broad-spectrum antibacterial and antifungal activity. The transparent dressing acts as a barrier to protect the venipuncture site, effectively blocking external contamination, including fluids (waterproof), bacteria, virus and fungi.

In vitro tests have demonstrated that: The transparent film of Tegaderm CHG dressing can block viruses of up to 27nm or larger diameter in intact and unbroken conditions. The barrier to viruses is based on the physical properties of the dressing, rather than the auxiliary properties of CHG.

In vitro tests for germicidal time and inhibition zone proved that: The gel pad in Tegaderm CHG dressing is inhibitory to a wide range of gram-positive/negative bacteria and yeasts. Tegaderm CHG dressings are transparent for continuous observation of the puncture site and are breathable to allow moisture to escape.

The control product is a CHG-free transparent dressing used to cover and protect the catheterization site on the body surface and to secure the device to the skin, without any antibacterial ingredients, which is the currently most commonly used transparent dressing in DVC care in China.

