19.0 STATISTICAL CONSIDERATIONS

This is a prospective, randomized, open-label, parallel-group controlled, single-center study designed to explore whether the subject product effectively reduces bacterial colonization in comparison with the control product. Subjects will be divided into two groups based on the random number table.

For continuous data, descriptive statistics will include the number of subjects, mean, standard deviation, median, minimum and maximum values. For categorical data, descriptive summaries will be made by frequency and percentage. Unless otherwise specified, a two-sided test will be used for all statistical tests, and a p-value of less than 0.05 will be considered statistically significant for the difference being tested.

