19.1 Statistical Hypotheses

19.2 Sample Size Determination

This study will use a positive two-sided Z test for continuity calibration and use the O'Brien-Fleming expenditure function to determine the test boundary. Assuming a baseline value of 18.7% for CVC tips colonization rate in the control group (this figure is reported by a domestic epidemiological survey) and a reduction rate of 50.0%, each group should contain at least 220 patients with CVC to reach 80% likelihood at 5% significance level. A total of 440 valid cases are required in both groups combined. An interim analysis is scheduled for this study and will be conducted after completion of follow-up visits of 220 subjects to correct for the pre-defined sample size.

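### Skin cultures for the primary endpoint are taken by departmental routine with no required neutralisation of residual chlorhexidine, so carry-over could favour the test dressing

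*Protocol*

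**What the plan says.** Skin culture is part of the primary endpoint. Protocol 5.1 and 5.3.1 and SAP 2.1, 4.1.1 and 6.3.1 all define it as culture positivity of the CVC tip and of the skin at the insertion site after removal. Section 8 of the SAP lets a result on either one count towards early stopping.

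The sampling instruction is one item in Protocol 10.2.4. The tip is cut with sterile scissors, "skin sampling around the insertion site is performed", and the samples go aseptically for pathogen testing and species analysis, all by the department's usual practice. No swab, transport medium, neutraliser, site preparation or culture method is named there or in the SAP.

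The two dressings differ in one respect that bears on culture. Protocol 3.0 gives the test dressing 15 to 78 mg of CHG in its gel pad, depending on model; the control has no antibacterial ingredient. From laboratory tests of killing time and zones of inhibition, Protocol 2.1 concludes: "The gel pad in Tegaderm CHG dressing is inhibitory to a wide range of gram-positive/negative bacteria and yeasts".

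**The concern.** The trial asks whether the dressing reduces organisms on the patient. The endpoint records whether organisms grow in the laboratory. The two agree only if nothing in the sample stops growth after collection. Skin around the insertion site has been beneath the dressing until the catheter comes out, and in the test arm that dressing carries an agent which, by the protocol's own account, inhibits growth in vitro. If some CHG travels with the sample, a negative culture may mean inhibition in the laboratory rather than clean skin.

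Pad-derived error of this kind arises after randomisation, falls in one arm and points in the direction of the hypothesis. The planned analyses cannot remove it. The chi-square or Fisher test, the mixed model, the FAS and PPS, and the results with and without filling of missing values all use the same recorded culture result. A larger sample would not help either, because bias does not shrink with n.

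**Working it through.** **Inputs from the documents**
- Control tip rate: "Assuming a baseline value of 18.7% for CVC tips colonization rate in the control group" (Protocol 19.2).
- Effect and size: "a reduction rate of 50.0%, each group should contain at least 220 patients with CVC", "to reach 80% likelihood at 5% significance level" (Protocol 19.2). The test-arm tip rate is therefore 18.7% × 0.5 = 9.35%.
- Two-sided testing (Protocol 19.0), 1:1 allocation (Protocol 10.2.1), final threshold 0.048 (SAP 6.1).

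**Inputs assumed, because neither document gives them**
- s, the share of truly positive test-arm skin samples that CHG turns negative: 10%, 20%, 30%.
- p, the skin positivity rate: 30% or 50%.

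**Step 1: reproduce the plan's own figure**

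n = [z(1−α/2)·√(2p̄q̄) + z(0.8)·√(p₁q₁ + p₂q₂)]² / (p₁ − p₂)², with p₁ = 0.187, p₂ = 0.0935, p̄ = 0.14025.
- α = 0.05: (1.960 × 0.4911 + 0.8416 × 0.4866)² / 0.0935² = 215.3, so 216 per arm.
- α = 0.048: (1.977 × 0.4911 + 0.8416 × 0.4866)² / 0.0935² = 218.0, so 219 per arm.

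Both are close to the stated 220, and power at 220 per arm is 80.8% and 80.4%. The plan describes a "positive two-sided Z test for continuity calibration"; with a continuity correction the result would be 237 or 239. That is a separate matter and does not affect this point. The bias calculation uses n = 220 and α = 0.048.

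**Step 2: false-positive rate under carry-over**

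With no true effect the control arm shows p and the test arm shows p(1 − s). The normal approximation to the chance of a significant result favouring the test arm is Φ[(d − 1.977·SE₀)/SE₁], where d = ps, SE₀ is the pooled and SE₁ the unpooled standard error.

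Example, p = 50%, s = 20%: rates 0.50 and 0.40, d = 0.10, SE₀ = √(2 × 0.45 × 0.55/220) = 0.0474, SE₁ = √((0.25 + 0.24)/220) = 0.0472. Then (0.10 − 1.977 × 0.0474)/0.0472 = 0.13, and Φ(0.13) = 55%. Summing exact binomial probabilities over all tables where the two-sided chi-square test rejects gives 56%.

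Exact two-sided rejection probability, no true effect:

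| Assumed skin rate | s = 10% | s = 20% | s = 30% |
|---|---|---|---|
| 30% | 10% | 29% | 58% |
| 50% | 18% | 56% | 89% |

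Without carry-over (s = 0) the rate is about 5%, as intended.

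**Step 3: effect on the estimate**

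If the true relative reduction is R, the observed one is 1 − (1 − R)(1 − s). An observed 50% then corresponds to a true R = 1 − 0.5/(1 − s): 44.4% at s = 10%, 37.5% at 20%, 28.6% at 30%.

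**Step 4: the interim rule**

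SAP section 8 asks for a difference above 50% and p below 0.005, on tip or skin, with other considerations also met. If the 50% is read as a relative reduction, carry-over of 10% to 30% alone gives an expected reduction of only 10% to 30%. By step 3, though, it lets a true skin effect well short of 50% look like one that meets the condition.

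**The case against.** The case against a stronger version of this point is good, and most of it stands.

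- **The tip.** A reader might infer that both samples come from under the pad. They do not. The dressing covers the skin; the tip lies in the vein, so CHG could reach it only indirectly, for instance on withdrawal through treated skin. This matters because the sample size and the re-estimation in Protocol 19.5 rest on the tip rate. The step 2 calculation at 18.7% gives about 8%, 18% and 36%, but that applies a skin mechanism to a tip rate and should not be used as evidence.
- **Silence is not omission.** The documents do not say that neutralisation is left out. The laboratory's own procedure may include it. What can be said is that the plan does not require it.
- **Not necessarily the test arm alone.** Exclusion criterion EC-4 lists CHG among the trial's products without tying it to one arm, so CHG from skin disinfection may be present in both. Cleaning before sampling is also possible. Either could change the difference between arms. The pad remains an additional source in the test arm only.
- **In vitro evidence.** The inhibition tests concern the pad itself. They do not show that residue on a skin sample blocks recovery. Fewer organisms on the skin is also what the device is meant to achieve, so a negative culture is not in itself suspect.
- **The percentages.** Both the suppression share and the skin rate are chosen, not sourced.

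None of this removes the core. Skin culture is a named part of the primary endpoint, its method is left open, and pad carry-over, if it occurs, can only favour the test device.

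**Conclusion.** The point holds for the skin component: a culture-based primary endpoint compares a dressing containing a growth inhibitor with one that has none, and the plan does not require the inhibitor to be neutralised in the sample. For the tip the concern is secondary.

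The size cannot be derived from the documents. The illustration shows only that modest suppression would matter: at 20%, the false-positive rate would be 29% or 56% at assumed skin rates of 30% or 50%, instead of about 5%. These figures assume no true effect, 220 evaluable skin samples per arm, suppression in the test arm alone and a final test at 0.048. They do not estimate this trial's risk, and CHG use in both arms would change them.

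A reader might go further and conclude that the trial cultures without neutralisation, or that a positive result would be an artefact. The documents support neither. They support asking for the method to be fixed before samples are taken, because a culture result cannot be corrected afterwards.

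**What to change.** In Protocol 10.2.4 item 4, replace the reference to departmental routine, for skin samples, with one written procedure used identically in both arms, with collection and transport in a CHG-neutralising medium. Apply the same to tip samples where it is compatible with the tip culture method. The documents do not state that method for the primary endpoint; the only tip criterion they give, a semi-quantitative count of at least 15 cfu in Appendix B, belongs to the CRBSI diagnosis. If the laboratory already neutralises, a sentence naming the medium and confirming its use in both arms settles the point.

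The cost is a different swab or transport medium for about 440 subjects, and a laboratory check that the neutraliser inactivates CHG and does not itself affect recovery. No visit or patient is added and the sample size is unchanged. If carry-over is fully removed, the false-positive rate returns to the planned 4.8%, and power for a true halving of the tip rate remains 80.4% at 220 per arm.

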10.3 Schedule of Events

A schedule of events is in the table below:

Table 10.3-1: Schedule

| Process | Screening and enrollment Day 0 | Dressing change visits | End-of-treatment visit ¹ | Withdrawal or discontinuance of visits ² |
|---|--------------------------------|------------------------|-------------------------------------|---|
| Informed consent collection | X | | | |
| Assessment of inclusion/exclusion criteria | X | | | |
| Randomization | X | | | |
| Demographic data ^a | X | | | |
| Previous medical history | X | | | |
| Vital signs ^b | X | | X | X |
| Routine blood examination ^c | X | | X | X |
| Record of deep vein catheterization | X | | X | X |
| Skin assessment around the catheter site | X | X | X | X |
| Dressing application or change (multiple times) | X | X | | |
| Documentation of relevant concomitant medication | X | X | X | X |
| Evaluation of subject product (dressing edge curling, etc.) | | X | X | X |

| | | | | |
|---|---|---|---|---|
| Total duration of catheterization | | | X | |
| Total duration of test/control dressing use | | | X | |
| Catheter-tip bacterial culture | | | X | |
| Bacterial culture from skin samples around the insertion site | | | X | |
| Blood bacteriological culture | | | X | |
| AE/SAE | X | X | X | X |
| Device defects | X | X | X | X |

Note:

- a: Date of birth, gender, ethnicity, height, weight, etc.;
 - b: Pulse, blood pressure, respiration, temperature;
 - c: Red blood cell (RBC) count, white blood cell (WBC) count, neutrophil ratio, hemoglobin, platelets, C-reactive protein, etc.;
- 1: There may be multiple visits documented when multiple deep vein catheters are removed in succession;
 2. For subjects withdrawing from or discontinuing the trial.

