3.3 Risks and Benefits of the Device(s) Used in this Study

3.3.1 Risks of the Device

Dressings are considered to be low-risk medical devices and are commonly used in health care and at home with few problems reported. Potential risks to subjects include possible localized skin irritation: such as itching, erythema and rash, some minor pain and erythema during removal, contact dermatitis and systemic allergic reactions, and skin stripping without any long-term effect. If the investigator discovers any erythema symptom equal to or greater than Grade 3 (0-4 scale; see Appendix B for grading details), or if any allergic reaction occurs, its use shall be discontinued for that subject.

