3.3.5 Mitigation of Risk

Risk related to the device may be mitigated or controlled through appropriate selection of study subjects for inclusion into this study, adherence to this Clinical Investigation Plan, and reporting of Adverse Events, Device Deficiencies and deviations to the Sponsor. If the subject experiences any discomfort, the

investigators could discontinue the clinical trial and conduct appropriate treatment and care based on clinical judgment.

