9.2 Point of Exit

Study subjects may exit the study for a variety of reasons. The Investigator shall record the reason for withdrawal and discontinuation of the study in the applicable Case Report Form. These reasons include, but are not limited to:

- Study completion (all study related visit(s) are completed)
- Withdrawal by the Subject
- Withdrawal by Investigator
- Lost to follow-up
- Death
- Study Termination

If a subject withdraws or discontinues participation before study completion, the subject will not be accounted into the per protocol set (PPS) analysis until the required enrollment is reached but will be accounted into the safety set analysis.

[figure not shown]
Data collected until the last known contact of study subject may be used in the analysis of study data. Because the subjects in this study are all ICU patients, patients will be considered lost to follow-up if they are transferred out of the ICU or discharged without removal of the CVC. If the study subject withdraws from the study for any reason and there is an ongoing safety event, additional safety event information may need to be collected by the Investigator and shared with Sponsor.

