6.4 Safety Evaluation

- (1) Evaluation Indicators
 - 1) Adverse events;
 - 2) Vital signs: including temperature, respiration, pulse, systolic blood pressure, diastolic blood pressure;
 - 3) Laboratory Check: Blood routine:
 - 4) Effects on the skin of the covered area, e.g. local infection, local skin irritation.
- (2) Evaluation method

Safety analysis was performed using the safety analysis population (SS).

The adverse event was coded according to the latest edition of the Medical Dictionary for Regulatory Activitie (MedDRA). Adverse events that occurred prior to randomization will be listed in the list only.

The analysis of AE will be based on Treatment Emergent Adverse Event (TEAE) during the treatment period. Any AE after the first application of the investigational device, whether or not related to the investigational device, will be defined as a TEAE, as will an AE that existed prior to the application of the investigational device but that worsens during the treatment period. In cases where AE cannot be defined as occurring before the first application of the investigational device or after the first application of the investigational device of the investigational device, AE will be classified as occurring after the first application of the investigational device as the most conservative approach.

The number of cases, case times, and percentages of all TEAEs, TEAEs belonging to CLABSI, TEAEs belonging to CRBSI, and TEAEs occurring in association with the investigational device are tabulated and summarized by system organ (SOC), preferred term (PT), and severity, respectively, for each group. Multiple occurrences of the same adverse event in the same participant will be summarized using the most severe one for severity and relevance to the investigational device.

TEAEs leading to study discontinuation, serious adverse events, and adverse events leading to death were summarized for each group by system organ (SOC), preferred term (PT), respectively, in descending order of the number of cases occurring in the test group.

Adverse events associated with the investigational device included a relationship to the investigational device determined to be: "relevant", "may be relevant".

Adverse events that led to study discontinuation included the choice of measures taken for the investigational device as: "Permanent deactivation of the investigational device".

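### The plan does not say whether a patient whose study dressing is stopped is still cultured at CVC removal, and the withdrawal visit schedules no tip or skin culture

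*Protocol*

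**What the plan says.** **Schedules.** Protocol Table 10.3-1 has "Catheter-tip bacterial culture | | | X" and "Bacterial culture from skin samples around the insertion site | | | X". In both rows the only mark is at the end-of-treatment visit. Total catheterization time and total dressing time are marked the same way. The fourth column, whose footnote reads "For subjects withdrawing from or discontinuing the trial", is blank for all four rows. SAP Table 3.1 has the same pattern.

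**Stopping the dressing.** Protocol 3.3.1 ends use of the dressing for erythema of grade 3 or more, "or if any allergic reaction occurs, its use shall be discontinued for that subject". Protocol 3.3.5 says that if a subject has discomfort, "investigators could discontinue the clinical trial and conduct appropriate treatment and care based on clinical judgment".

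**Stopping the study.** SAP 6.4 sets the rule for tabulating events: "Adverse events that led to study discontinuation included the choice of measures taken for the investigational device as" a permanent stop of that device. Protocol 9.2 gives an open-ended list of exit reasons that does not name stopping the dressing. It leaves out of the PPS anyone covered by "If a subject withdraws or discontinues participation before study completion". Protocol 10.2.4 ties the end-of-treatment visit to catheter removal and says that the trial is not complete before the CVC is out.

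**Missing endpoint.** Protocol 19.3 and SAP 5.1 apply a worst-case fill in the FAS, the primary set. SAP 7.3 defines the fill as positive and asks for the unfilled result as well. Protocol 19.6 says that efficacy data will not be imputed, and leaves details to the SAP.

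**The concern.** Stopping a dressing does not remove the catheter. The patient is still in the same ICU, and cutting the tip at removal is departmental routine (Protocol 10.2.4). The primary endpoint can therefore usually still be observed. Whether it is observed depends on how the site reads five sections that do not agree: Protocol 3.3.1, 3.3.5, 9.2 and 10.2.4, and SAP 6.4.

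If the patient is handled as a withdrawal, the schedule asks for no culture. In the FAS, a skin reaction then becomes a recorded colonization, whatever the tip would have grown. The PPS and the unfilled result leave the patient out. None of these is the observed outcome under the assigned dressing, which is what a set described as intention-to-treat should use. The sample size has no margin for this: 440 are to be enrolled and 440 valid cases are required.

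The loss may also differ by arm. Only the test dressing contains CHG, and the trial is open-label.

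**Working it through.** **1. The sections side by side**

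| Section | What it implies after the dressing is stopped |
|---|---|
| Protocol 3.3.1 | Use of the dressing ends; follow-up not mentioned |
| Protocol 3.3.5 | The investigator may end the trial for that subject |
| Protocol 9.2 | Dressing stop not named as an exit; list not exhaustive |
| Protocol 10.2.4 | Trial not complete until CVC removal, when cultures are taken |
| SAP 6.4 | A permanent device stop marks study discontinuation |

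Two courses are open. Under 10.2.4 alone, the patient stays in and is cultured. Under 3.3.5 or SAP 6.4, the patient goes to the withdrawal visit and is not cultured. No section chooses between them.

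**2. Inputs for the size**

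- Protocol 19.2: control rate 18.7%; 50% reduction, so test rate 9.35%; 220 per arm; 80% power; 5% two-sided.
- SAP 6.1: final two-sided alpha 0.048, so z = 1.977.
- SAP 7.3: a missing endpoint is counted as positive.
- Assumed, because the documents give no figure: the share m of an arm with no culture, at 1%, 2% or 3% (about 2, 4 or 7 of 220).

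**3. The plan's own figure**

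The pooled two-proportion Z test without continuity correction needs 216 per arm at alpha 0.05 and 219 at 0.048, against the stated 220. Power at 220 and alpha 0.048:

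- s0 = √(2 × 0.14025 × 0.85975 / 220) = 0.0331
- s1 = √((0.187 × 0.813 + 0.0935 × 0.9065) / 220) = 0.0328
- power = Φ((0.0935 − 1.977 × 0.0331) / 0.0328) = 80.4%

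The continuity correction that Protocol 19.2 appears to describe would need 237 per arm at alpha 0.05. That is a separate matter, and the uncorrected test is used below.

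**4. Effect of the fill**

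Rate after the fill: q = m + (1 − m)p. Example with 2% in both arms: control 0.02 + 0.98 × 0.187 = 0.203; test 0.02 + 0.98 × 0.0935 = 0.112; power = Φ((0.0916 − 1.977 × 0.0347) / 0.0345) = 75%.

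| Assumed loss, test / control | Test rate | Control rate | Apparent reduction | Power |
|---|---|---|---|---|
| 0 / 0 | 9.35% | 18.7% | 50% | 80% |
| 1% / 1% | 10.3% | 19.5% | 47% | 78% |
| 2% / 2% | 11.2% | 20.3% | 45% | 75% |
| 3% / 3% | 12.1% | 21.1% | 43% | 72% |
| 1% / 0 | 10.3% | 18.7% | 45% | 71% |
| 2% / 0 | 11.2% | 18.7% | 40% | 60% |
| 3% / 0 | 12.1% | 18.7% | 35% | 48% |

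**5. Direction**

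Test-arm-only loss with the fill works against the test dressing. With no true effect (18.7% in both arms) and 2% test-arm loss, the chance of a significant result favouring CHG is 0.8%, against a nominal 2.4%.

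The unfilled result can err the other way. If 5% of the test arm is lost and, by assumption, 30% of those were colonized, the observed test rate is (0.0935 − 0.05 × 0.30) / 0.95 = 8.3%. The apparent reduction is then 56% instead of 50%. If the loss is unrelated to colonization, the unfilled result keeps the 50% reduction and, at 1% to 3% test-arm loss, about 80% power.

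**The case against.** The best defence is that the protocol never makes stopping the dressing an exit. Section 3.3.1 stops a product, the footnote to the withdrawal column covers only those leaving the trial, and 10.2.4 carries the trial to CVC removal. SAP 6.4 is a rule for an adverse-event table and does not govern follow-up. This stands against the stronger reading that the plan has ruled these patients out of the study. It does not close the gap, because 3.3.5 permits ending the trial for a subject and no sentence requires culture after a dressing stop.

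A reader might also infer that the loss is selective by arm. The documents do not show this. Protocol section 2.0 says that the risk of skin reactions is no higher than with comparable products. Section 3.3.2 calls CHG reactions occasional or rare, EC-4 excludes known sensitivity, and adhesive reactions can occur in either arm. The loss may differ by arm; no more can be said.

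Nor is it established that withdrawn subjects lack catheter-days. The withdrawal column includes the catheterization record, and the SAP uses insertion and withdrawal dates, so time to withdrawal looks derivable.

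The power loss comes mainly from the positive fill, and SAP 7.3 already asks for the unfilled result. Both points are correct. But the unfilled result is unbiased only if the loss is unrelated to colonization, and an observed culture needs no such assumption.

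Finally, a blank cell is right for patients who leave the ICU with the CVC in place, since there is no tip to culture. The fix has to allow for that.

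**Conclusion.** The point holds as an inconsistency that should be fixed. Both schedules omit the primary-endpoint cultures from the withdrawal column, and the sections on stopping the dressing, ending the study and completing follow-up do not agree. An obtainable endpoint can therefore go uncollected and enter the primary analysis as a positive.

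The size depends on loss rates that the documents do not give. At an assumed equal loss of 1% to 3% per arm, power falls from 80% to between 78% and 72%. The 71% to 48% range puts all the loss in the test arm. It is a one-sided worst case, biased against the test dressing, and not a forecast. All these figures assume the planned rates, 220 per arm, alpha 0.048, the uncorrected Z test and the positive fill.

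**What to change.** Leave the rule for stopping the dressing unchanged, and reconcile Protocol 3.3.1, 3.3.5, 9.2 and 10.2.4 with SAP 6.4.

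- State that stopping the study dressing is separate from leaving the study. Tip culture, skin culture, total catheterization time and total dressing time are obtained whenever the CVC is removed in the ICU, unless consent is withdrawn.
- Mark this in Protocol Table 10.3-1 and SAP Table 3.1, with a note that it does not apply to patients who leave the ICU with the CVC in place.
- Analyse these cultures in the FAS in the assigned arm.
- Reword SAP 6.4 so that a permanent device stop means discontinuation of the dressing and not of the study.
- Report missing cultures by arm and reason.

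The cost is an amendment to the text and both tables, and a few more cultures of the kind already taken from every completer. The FAS will include some cultures taken after the dressing was stopped, which is what an intention-to-treat comparison intends. A tip that was not cultured at removal cannot be recovered later, so the change is worth making early.
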